## Abbreviations

cm	centimeter
dFLA	dynamic functional leg alignment
fKROM	frontal knee range of motion
GRAIL	Gait Real-time Analysis Laboratory
ICC	Intraclass Correlation Coefficient
kg	kilogram
LW	level walking
m	meter
OA	osteoarthritis
vGRF	vertical ground reaction force

# **Synopsis**

## **Title of the project**

Up & Down - Effects of real-time feedback during decline walking on kinematic and kinetic gait parameters

## **Short summary**

Control of the dynamic functional leg alignment (dFLA) and biomechanical load are important joint related aspects regarding the development of osteoarthritis (OA). Research on level walking with feedback on load related parameters provided innovative treatment possibilities. Concerning walking on sloped surfaces, fundamental biomechanical knowledge exists. However, deeper insights into the control of the dFLA during decline walking, and the usefulness of real-time feedback are missing. This study is set up as cross-sectional observation of gait under four conditions, which follows a randomized sequence in order to avoid carry over effects. Thirty (30) participants aged between 18 and 35 years will be included. They will complete a three-dimensional gait analysis on a 5-m ramp with 10° inclination. Afterwards they will be observed under four different conditions a) self-paced walking b) self-paced walking with internal focus of

attention, c) self-paced walking with real-time feedback, and d) condition c speed-matched walking, on a 10° declined split belt treadmill. The primary outcome parameter will be the frontal knee range of motion (fKROM). Secondary outcomes include the ground reaction force loading rate, spatial-temporal parameters, sagittal frontal and transversal kinematics, and kinetics for the lower extremities.

The findings should improve the understanding of effects of real-time feedback on the control of the dFLA and lower limb loading. Results will be published in a peer-review journal.

# Rationale and background information

The prevalence of symptomatic osteoarthritis (OA) was estimated to be about 3-9% in European adults aged over 19 and increases towards to 9-15% in those over 60 years. Biomechanical loading was identified as one of highly relevant parameters concerning the development of knee OA and the management of conservative OA therapy. In this context, kinematic and kinetic parameters have been studied thoroughly during level walking. Previous studies reported on altered gait parameters in incline and increasing inclination walking. However, declined walking is, due to higher vertical ground reaction forces (vGRF), even more challenging for the musculoskeletal system^6-8 and the control of the dynamic functional leg alignment (dFLA). Especially knee and hip joint compression forces increase with the grade of inclination. The medio-lateral load distribution and loading velocity generally is associated with knee valgus / varus thrust, which was reported for level walking (LW) up to 6° in healthy persons. Beside one x-ray based study data for declined walking is missing. As loading and neuromuscular control have been shown to be important in the prevention and treatment of knee OA, feedback is an effective tool supporting patients. Especially real-time feedback targeting at the sensorimotor control of the dFLA during walking has not been investigated yet.

Assessment of uphill or downhill locomotion has mainly been studied using instrumented ramps. Only few studies have been done on instrumented treadmills with inclination. But in those the kinetic measurement technology is not sufficient comparable. Furthermore, knowledge on the agreement of ramp and treadmill derived kinetic and energy data is missing.

To our knowledge, the influence of motor control interventions as internal focus of attention and real-time feedback on prior mentioned biomechanical factors in declined walking have not been studied before.

## Study goals and objectives

This cross-sectional observation of decline walking under four conditions, aims at enhancing the understanding of the effects of real-time feedback on lower limb gait kinematics and kinetics. Furthermore, the agreement of kinematic and kinetic parameters of 10° decline and incline walking between ramp and treadmill will be assessed.

The primary research question is, whether real-time feedback alters the frontal knee range of motion when compared to self-paced walking on the one hand, and matched speed walking on the other hand. The secondary aspect focuses on the effect of lower limb loading in decline walking. Thirdly, parameters of interest will be compared between declined/inclined ramp and declined/inclined treadmill walking. Consequently, underlying hypotheses were phrased as follows:

Primary null hypothesis: Means of the outcome "frontal knee range of motion" are equal across the four conditions a) self-paced walking, b) self-paced walking with internal focus of attention, c) self-paced walking with real-time feedback, and d) condition c speed-matched walking. Predefined contrasts hypothesize that:

- 1) The outcome of self-paced walking with internal focus of attention and self-paced walking with real-time feedback is equal to speed matched walking ( $bc=d$ )
- 2) The outcome of self-paced walking with internal focus of attention and self-paced walking with real-time feedback is equal to self-paced walking ( $bc=a$ )
- 3) The outcome of self-paced walking with real-time feedback is equal to self-paced walking with internal focus of attention ( $c=b$ )

Primary alternative hypothesis: Means of the outcome "frontal knee range of motion" are NOT equal across the four conditions a) self-paced walking, b) self-paced walking with internal focus of attention, c) self-paced walking with real-time feedback, and d) condition c speed-matched walking. Two-sided testing will be applied, as knowledge from existing literature is only moderate. Predefined contrasts hypothesize that:

- 1) The outcome of self-paced walking with internal focus of attention and self-paced walking with real-time feedback is NOT equal to speed matched walking ( $bc \neq d$ )
- 2) The outcome of self-paced walking with internal focus of attention and self-paced walking with real-time feedback is NOT equal to self-paced walking ( $bc \neq a$ )
- 3) The outcome of self-paced walking with real-time feedback is NOT equal to self-paced walking with internal focus of attention ( $c < b$ )

Secondary null hypothesis: Means of the outcome "ground reaction force loading rate" are equal across the four conditions a) self-paced walking, b) self-paced walking with internal focus of attention, c) self-paced walking with real-time feedback, and d) condition c speed-matched walking. Predefined contrasts are for this outcome concordant with those of the primary hypothesis.

Secondary alternative hypothesis: Means of the outcome "ground reaction force loading rate" are NOT equal across the four conditions a) self-paced walking, b) self-paced walking with internal focus of attention, c) self-paced walking with real-time feedback, and d) condition c speed-matched walking. Two-sided testing will be applied, as knowledge from existing literature is only moderate. Predefined contrasts are for this outcome concordant with those of the primary hypothesis.

Tertiary null hypothesis:

- 1) The agreement of continuous kinematic and kinetic outcomes of the lower limb (see list of outcome parameters) between decline ramp walking and speed-matched decline treadmill walking is lower than 0.75 (ICC).
- 2) The agreement of continuous kinematic and kinetic outcomes of the lower limb (see list of outcome parameters) between decline ramp walking and self-paced decline treadmill walking is lower than 0.75 (ICC).
- 3) The agreement of continuous kinematic and kinetic outcomes of the lower limb (see list of outcome parameters) between incline ramp walking and speed-matched incline treadmill walking is lower than 0.75 (ICC).
- 4) The agreement of continuous kinematic and kinetic outcomes of the lower limb (see list of outcome parameters) between incline ramp walking and self-paced incline treadmill walking is lower than 0.75 (ICC).

Tertiary alternative hypothesis:

[figure not shown]
- 1) The agreement of continuous kinematic and kinetic outcomes of the lower limb (see list of outcome parameters) between decline ramp walking and speed-matched decline treadmill walking is at least 0.75 (ICC).
- 2) The agreement of continuous kinematic and kinetic outcomes of the lower limb (see list of outcome parameters) between decline ramp walking and self-paced decline treadmill walking is at least 0.75 (ICC).
- 3) The agreement of continuous kinematic and kinetic outcomes of the lower limb (see list of outcome parameters) between incline ramp walking and speed-matched incline treadmill walking is at least 0.75 (ICC).
- 4) The agreement of continuous kinematic and kinetic outcomes of the lower limb (see list of outcome parameters) between incline ramp walking and self-paced incline treadmill walking is lower at least 0.75 (ICC).

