## Methods/Design

### Trial design

The study is set up as cross-sectional observation of gait under four conditions, which follows a randomized sequence in order to avoid carry over effects. Chronologically, the assessments will start with the tertiary observation, investigating agreements between declined/inclined ramp and treadmill walking. Thereafter, three out of four conditions (self-paced walking, self-paced walking with internal focus of attention, and self-paced walking with real-time feedback) are tested under block randomization of their six possible permutations (ABC, BCA, CAB, CBA, ACB, BAC). With three conditions ( $n=3$ ), this represents the smallest number of permutations, equaling a Williams design, where each condition precedes each other condition equally often and each treatment occurs equally

frequently at each position. The fourth corresponding condition (speed-matched walking), can technically not take place before the corresponding real-time feedback condition, and is therefore exempted from the sequence randomization and always follows after self-paced walking with real-time feedback. Numbers of participants assessed for eligibility, allocated to assessments, and analyzed will be recorded by a modified CONSORT flow chart, without consideration of losses to follow-up, due the cross-sectional study design. Figure 1 illustrates a flowchart of the trial design.

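### The primary question is about real-time feedback alone, but two of the three predefined contrasts join it with internal focus, and no weights are written

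*Combined protocol and SAP*

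**What the plan says.** Conditions are labelled as in the plan: a self-paced, b self-paced with internal focus of attention, c self-paced with real-time feedback, d walking matched to the speed of c.

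- **Question (Study goals and objectives).** "The primary research question is, whether real-time feedback alters the frontal knee range of motion when compared to self-paced walking on the one hand"; the sentence then adds matched-speed walking as the second comparator. The same section says that the study "aims at enhancing the understanding of the effects of real-time feedback on lower limb gait kinematics and kinetics". The title is "Effects of real-time feedback during decline walking on kinematic and kinetic gait parameters", preceded by the project name, and the Short summary ends: "The findings should improve the understanding of effects of real-time feedback on the control of the dFLA and lower limb loading". None of these mentions b.
- **Link to the hypotheses.** They are introduced by "Consequently, underlying hypotheses were phrased as follows".
- **Contrasts under the four-condition null.** Contrast 1 (bc=d): "The outcome of self-paced walking with internal focus of attention and self-paced walking with real-time feedback is equal to speed matched walking". Contrast 2 (bc=a): "The outcome of self-paced walking with internal focus of attention and self-paced walking with real-time feedback is equal to self-paced walking". Contrast 3 is c=b. The secondary outcome, loading rate, uses the same three.
- **Role of d (Trial design).** It "can technically not take place before the corresponding real-time feedback condition" and always follows it. It is the speed control for c.
- **Statistical analysis.** A one-factor repeated-measures ANOVA is planned, with contrasts for the listed hypotheses, two-sided alpha 0.05 and Bonferroni-Holm. Tests unrelated to the primary and secondary hypotheses are exploratory, and testing is confined to what the hypotheses pre-specify. No contrast coefficients are given.

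**The concern.** The question calls for two comparisons, c with a and c with d. Neither appears by itself in the list of contrasts. Feedback stands alone only against internal focus, which the question does not mention.

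If bc is an average, the confirmatory result describes a mixture of two different instructions: feedback on knee alignment and lengthening the spine. A significant bc−a could come entirely from internal focus and be reported as a feedback effect. A real feedback effect could be diluted, or cancelled if the two instructions act in opposite directions. Contrast 1 also loses its purpose, because d is matched to the speed of c while b is walked at its own self-selected speed.

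If bc means b and c separately, the right tests exist, but the number of comparisons and the Holm family are not written down. The plan does not say which reading applies, so the analyst has to choose.

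**Working it through.** **Plan figures.** Sample size estimation gives 25 analysable participants, 20% dropout and 30 recruited. 25 × 1.20 = 30 reproduces this; 30 × 0.80 = 24. The plan gives no effect size, SD, correlation or power, so there is no power figure to reproduce.

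**Step 1. Question against contrasts** (weights in the order a, b, c, d; bc taken as the average).

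| Comparison | Weights | Source |
|---|---|---|
| c−a | (−1, 0, 1, 0) | primary question |
| c−d | (0, 0, 1, −1) | primary question |
| bc−d | (0, ½, ½, −1) | contrast 1 |
| bc−a | (−1, ½, ½, 0) | contrast 2 |
| c−b | (0, −1, 1, 0) | contrast 3 |

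No listed contrast equals either comparison in the question.

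**Step 2. How they relate.**
- bc−a = ½(c−a) + ½(b−a), so contrast 2 is half about internal focus.
- (−1, ½, ½, 0) + ½(0, −1, 1, 0) = (−1, 0, 1, 0), so c−a = contrast 2 + ½ contrast 3.
- In the same way, c−d = contrast 1 + ½ contrast 3.

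Both comparisons can be estimated, but no test of either is planned on this reading.

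**Step 3. Relative sensitivity.** Assume equal variances s² and equal correlations r across conditions.
- Var(c−a) = 2s²(1−r).
- Var(bc−a) = (1 + ¼ + ¼)s²(1−r) = 1.5s²(1−r).
- If the effect of b is k times that of c, the standardised effect of bc−a relative to c−a is ((1+k)/2) × √(2/1.5).

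This gives 0.58 for k=0, 0.87 for k=½, 1.15 for k=1 and 0 for k=−1. It equals 1 at k≈0.73, above which pooling gains power.

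**Step 4. Power of a single test.** n=25, two-sided 0.05, noncentral t with 24 df. The standardised paired effect dz of c−a is assumed and shown over a range.

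| dz of c−a | direct c−a | bc−a, k=0 | bc−a, k=½ | bc−a, k=1 | bc−a, k=−1 |
|---|---|---|---|---|---|
| 0.3 | 0.30 | 0.13 | 0.24 | 0.38 | 0.05 |
| 0.5 | 0.67 | 0.28 | 0.55 | 0.79 | 0.05 |
| 0.6 | 0.82 | 0.38 | 0.70 | 0.91 | 0.05 |
| 0.8 | 0.97 | 0.60 | 0.91 | 0.99 | 0.05 |

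**Step 5. With Holm over three contrasts.** Simulation with 200,000 trials per case, except the k=½ and k=¾ rows, which are separate runs under the same assumptions. dz=0.584, which gives an unadjusted c−a 80% power at n=25.

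| Truth | n | bc−a rejects | direct c−a rejects |
|---|---|---|---|
| Only feedback works | 24 | 26% | 70% |
| Only feedback works | 25 | 27% | 72% |
| Only feedback works | 30 | 34% | 82% |
| Internal focus has half the effect | 25 | 54% | 68% |
| Internal focus has three quarters | 25 | 69% | 67% |
| Both equal | 25 | 82% | 67% |
| Both equal | 30 | 90% | 77% |
| Equal and opposite | 25 | 3% | 76% |

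If only internal focus works, bc−a rejects in 27% of trials at n=25 (34% at n=30) although feedback does nothing.

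If only feedback works and n=25, the ANOVA rejects in 84% of trials. A c−a difference can be deduced from the listed contrasts, with bc−a and c−b both significant in the same direction, in 21%. In 63% the ANOVA rejects but c−a cannot be deduced in this way. Requiring a significant ANOVA first moves the n=25 figures for bc−a and direct c−a by less than 2 points.

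**The case against.** The strongest reply has five parts.

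1. *Equal weights are the ordinary reading of bc, so missing weights are only a clarification.* Fair for the pooled reading. The mismatch with the question remains.
2. *bc may mean b and c each, since the hypotheses are said to follow from the question.* Possible, and then c−a and c−d are covered. But there are five comparisons where the plan lists three, and the Holm family is unwritten. The documents do not settle this.
3. *Feedback is still tested: the four-condition null is primary, c=b isolates feedback against another instruction, and the Rationale treats both instructions together as motor control interventions.* This gives pooling a rationale. However, the ANOVA does not say which conditions differ, c=b is not a comparison the question asks for, and a deliberate pooled aim would require a different primary question.
4. *c−a and c−d can be reported as exploratory, and no data are lost.* Correct, and this bounds the harm. It still leaves the stated primary question without its own confirmatory answer.
5. *The headline percentages use one assumed effect and the case least favourable to pooling.* Fair. The loss shrinks as internal focus becomes more effective and turns into a gain above about 0.73 of the feedback effect. At dz 0.3 both tests are weak. The percentages illustrate the consequence; the argument does not depend on them.

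**Conclusion.** The concern holds. The stated primary question and the predefined contrasts do not match, for frontal knee range of motion and, through the shared contrasts, for loading rate. On the pooled reading the confirmatory tests answer a different question; on the separate reading the test family is undefined. That conclusion rests on the text and the algebra alone.

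The practical size depends on unknown effects. Under the assumptions above at n=25, it runs from a large loss when only feedback works (27% against 72%), through parity at about three quarters, to a gain when both instructions work equally (82% against 67%). The fault is in what is being tested, not in power as such: even where pooling gains power, rejecting bc=a does not by itself show that feedback differs from self-paced walking. Because this is the primary confirmatory analysis, it should be corrected, although the harm is limited by every participant walking under all four conditions.

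**What to change.** Write the contrast weights and the Holm family into Study goals and objectives and Statistical analysis, for both outcomes, choosing according to intent.

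- **Feedback is the question (preferred, as it matches the stated question).** Use c−d (0, 0, 1, −1), c−a (−1, 0, 1, 0) and c−b (0, −1, 1, 0), with a Holm family of three per outcome. Label the pooled contrasts exploratory. The number of tests does not change. The cost is that the pooled contrasts lose confirmatory status, and power is lower if both instructions work equally (67% for c−a against 82% for bc−a at n=25).
- **bc meant b and c separately.** Write out c−d, c−a, b−d, b−a and c−b, with a Holm family of five. Power for c−a when only feedback works falls from 72% to 60% at n=25 and from 82% to 71% at n=30.
- **The pooled effect is the question.** Keep bc = (b+c)/2, write its weights, and reword the primary research question to name both instructions.

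In each case state whether Holm is applied per outcome or across both. The plan does not say, and the power figures here assume per outcome. The change is one of wording and a contrast matrix; no new data or participants are needed.

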## Statistical analysis

All metric parameters will be analyzed with SPSS 26 (IBM Corporation, Armonk, NY, USA). Data will be tested for normality using the Shapiro-Wilk Test, and graphical inspections of Q-Q-plots. Differences between ramp-walking and matched speed / self-paced walking on the inclined / declined treadmill will be analyzed using paired two-tailed t-test and tested for agreement using ICC [3.1, absolute agreement, single measures] with SEM of the ICC. To evaluate differences between the four conditions (decline walking, internal focus of attention, real-time feedback, and matched speed walking), a one-factorial analysis of variance with repeated measures will be used. Contrasts will be employed to test aforementioned pre-specified hypotheses. In view of the legitimization given with the hypothesis, two-sided testing will be applied. One-dimensional statistical parameter mapping (1dSPM) will be used to examine the steady parameters of the gait analysis. All other statistical tests than those related to the primary and secondary hypotheses are considered exploratory and statistical testing will be limited to tests as pre-specified by the hypotheses. Consequently, Bonferroni-Holm method will be used in terms of correcting for multiple testing. Alpha will be set to 0.05; exact p-values will be reported though.

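### The hypothesis labelled primary is a four-condition F test that internal focus or speed-matched walking alone can reject, and no rule says which test decides the feedback question

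*Combined protocol and SAP*

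**What the plan says.** Study goals and objectives asks "whether real-time feedback alters the frontal knee range of motion when compared to self-paced walking on the one hand, and matched speed walking". In symbols the question is c versus a and c versus d.

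The hypotheses that follow are broader. The primary null is that the mean frontal knee range of motion values "are equal across the four conditions a) self-paced walking" and the other three conditions; the alternative is that they "are NOT equal across the four conditions a) self-paced walking" and the rest. Three contrasts are listed under this hypothesis: the combination of b and c against d, the same combination against a, and c against b ("The outcome of self-paced walking with real-time feedback is equal to self-paced walking with internal focus of attention"). Neither c−a nor c−d is listed on its own. The loading-rate hypotheses in the same section take over this structure.

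Statistical analysis says that "a one-factorial analysis of variance with repeated measures will be used. Contrasts will be employed to test aforementioned pre-specified hypotheses". It sets two-sided testing, alpha 0.05 and a Bonferroni-Holm correction. It does not list the Holm family, say whether the F test must be significant before the contrasts are read, or say which result counts if they differ.

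Trial design and Limitations and problems anticipated both state that condition d is outside the randomised sequence. Trial design places it after c.

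**The concern.** The omnibus alternative is true whenever any two of the four means differ, including the pairs a–b, a–d and b–d, none of which contains feedback. This is a practical risk. The rationale treats internal focus and feedback alike as motor control interventions, so b may well change gait. Condition d has a fixed place after c, so an order or carry-over shift in d is also plausible.

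Two things are at stake. Rejecting the hypothesis labelled primary need not say anything about feedback. And if the F test and the contrasts disagree, two analysts could both follow the plan and reach opposite primary conclusions.

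**Working it through.** **Inputs.** From Sample size estimation and study population: 25 evaluable participants, 20% dropout, 30 recruited. The plan's figure reproduces as 25 × 1.2 = 30. (Dividing instead, 25 / 0.8 = 31.25, gives 32; this is not the issue here.) The plan gives no effect size, SD or power. Assumed here: equal correlations between conditions, paired-difference SD of 1, and one condition shifted by δ in those SD units.

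**F test.** The error variance is half the paired-difference variance, 0.5. Shifting one of four means by δ gives a sum of squared deviations of 0.75δ². The noncentrality is therefore λ = n × 0.75δ² / 0.5 = 1.5nδ², with 3 and 3(n − 1) degrees of freedom.

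| δ | λ at n = 25 | F rejects, n = 25 | F rejects, n = 30 |
|---|---|---|---|
| 0.3 | 3.375 | 29.1% | 34.8% |
| 0.5 | 9.375 | 70.5% | 79.4% |
| 0.8 | 24.0 | 98.8% | 99.7% |

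λ does not depend on which condition moves, so the F test cannot separate a feedback effect from a shift in b alone or d alone.

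**The three listed contrasts.** If only b shifts by 0.5, (b+c)/2 − d = 0.25, (b+c)/2 − a = 0.25 and c − b = −0.5: all three are non-zero with no feedback effect. If only d shifts by 0.5, the first equals −0.5 and the others are 0.

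**Simulation** (40,000 trials per row, n = 25, δ = 0.5, Holm over the three contrasts; repeated for this review with agreement to within about one percentage point):

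| Only condition shifted | F significant | At least one Holm contrast | F only | Contrast only |
|---|---|---|---|---|
| b | 71.0% | 62.1% | 11.8% | 2.9% |
| c | 70.6% | 61.5% | 12.0% | 2.8% |
| d | 70.6% | 64.0% | 10.5% | 3.9% |
| none | 5.2% | 4.9% | 2.2% | 1.9% |

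Disagreement between the two routes is 11.8 + 2.9 = 14.7% with b shifted and 12.0 + 2.8 = 14.8% with c shifted.

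**Direct contrasts.** The questions asked are combinations of the listed contrasts: c − a is the second plus half the third, and c − d is the first plus half the third. Neither is tested as such. Testing both with Holm over two, at least one is significant in 4.6% of trials when only b shifts and in 72% when only c shifts. When only d shifts, c − a rejects at its nominal 5%, but an unadjusted c − d test rejects in 67.0%.

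**Error rate with no effect.** If F at an unadjusted 0.05 and the Holm-adjusted contrasts both count as routes to rejection, the total is 4.9 + 2.2 = 7.1%. If F is one of four tests in the Holm family, it is about 4%.

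**The case against.** An overall F test followed by planned contrasts is ordinary practice. The contrasts are said to test the pre-specified hypotheses, which can be read as making them the tests of record. A competent reader would not take a significant F alone as proof of a feedback effect.

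Part of this stands. A reader might infer that the plan intends to report a significant F as evidence for feedback; it nowhere says so, and the null as written does not claim to be about feedback alone. But the equality of all four means is itself one of the pre-specified hypotheses, is the one labelled primary, and has its own test. The sentence on contrasts sets no hierarchy.

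A reader might also infer that making the listed contrasts decisive settles the matter. It does not. All three involve c, so restricting the decision to contrasts with c removes nothing, and they respond to a shift in b alone as often as to a shift in c alone (about 62% each).

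Finally, a reader might infer that the plan's error rate is inflated to 7%. That holds only if F is tested at an unadjusted 0.05 outside the Holm family. The documents do not define the family, so the figure belongs to one reading.

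**Conclusion.** The point holds. The test attached to the primary label does not answer the primary question, and the plan leaves open which result decides. For an assumed 0.5 SD shift at n = 25, the F test rejects in about 71% of trials whichever of b, c or d has moved, and the F test and the contrasts disagree in about 15%.

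The percentages rest on the assumed shift and on equal correlations; the range from 0.3 to 0.8 SD is 29% to 99%. The logical gap depends on neither. The documents do not show that b or d will in fact shift, only that the primary test could not tell such a shift from a feedback effect.

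**What to change.** In Study goals and objectives (primary and secondary hypotheses) and in Statistical analysis, state that:

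- the feedback claim is decided by the direct contrasts c−a and c−d, Holm-adjusted over these two at two-sided 0.05, with each comparison concluded separately;
- the omnibus F and the other contrasts are descriptive or supportive, so that a significant F alone is not a positive primary result;
- the same rule applies to loading rate;
- c−d is confounded with order, because d is always measured after c, and is interpreted with that caveat.

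This needs no extra participants or measurements. When only c shifts, the chance of at least one significant contrast rises from about 62% with the three listed contrasts to about 72%.

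The cost is that a significant F without a significant direct contrast can no longer be claimed as positive. That loses power when a and d differ from b = c in opposite directions: with each 0.3 SD away at n = 25, F rejects in about 69% of trials and at least one direct contrast in about 40%.
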